## 4.1.2 Secondary endpoints

- SDAI remission rate at Week 24
- SDAI remission rate at Week 48 in MTX Monotherapy Group

- ACR20, ACR50, and ACR70 response rate at each assessment timepoint
- HAQ remission rate at each assessment timepoint
- SDAI, CDAI, DAS28-ESR, and DAS28-CRP at each assessment timepoint, and change from baseline to each assessment timepoint
- Tender joint count, swollen joint count, VAS (physician- and patient-reported), HAQ, CRP, ESR, MMP-3, RF, and anti-CCP antibody at each assessment timepoint, and change from baseline to each assessment timepoint
- Modified total sharp score (mTSS) at each assessment timepoint, and change from baseline to each assessment timepoint
- Structural remission (mTSS  $\leq 0.5$ ) rate at each assessment timepoint
- Vital signs and laboratory findings at each assessment timepoint, and change from baseline to each assessment timepoint
- Status of AE (Up to Week 24, and up to Week 48 for each ARM)

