## 4.3 Bias

#### 4.3.1 Randomization

If a subject does not achieve to clinical remission (SDAI  $\leq$ 3.3) at Week 24 despite the maintenance of MTX dose at  $\geq$ 10 mg/week, the subject will start receiving ADA as an add-on therapy. Subjects then will be stratified by countries (Japan, South Korea, and Taiwan) as a stratification factor, and for each stratum, subjects will be randomized at a 1:1 ratio to either a group in which the MTD of MTX (10 to 25 mg/week) will be maintained (ARM-2), and a group in which the dosage of MTX will be reduced to 6 to 8 mg/week (ARM-3). Upon completion of Week 24 assessments, principal investigator/sub-investigator shall enter the Week 24 dosage of MTX, tender joint count (28 joints), swollen joint count (28 joints), VAS (physician- and patient-reported; 10 cm scale), and CRP in IWRS. If all necessary information is entered, a relevant treatment group in line with the status of randomization (ARM-1, ARM-2 or ARM-3) will be issued by IWRS.

The MTX dosage shall be either 6 mg/week or 7.5 mg/week in subjects in ARM-3 whose maintenance dose of MTX at Week 24 is 10 mg/week.

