## 9.2.1.2 Method of analysis for secondary efficacy endpoints

SDAI remission rate at Week 24, SDAI remission rate at Week 48 in MTX Monotherapy Group (ARM-1), ACR20, ACR50, and ACR70 response rates, HAQ remission rate, and structural remission rate at each assessment timepoint, and their two-tailed 95% confidence intervals will be calculated for each ARM. Furthermore, ARM-2 and ARM-3 at Week 48 will be compared using a stratified analysis with country as a factor.

Summary statistics (mean, standard deviation, median, and range) in each ARM at each assessment timepoint will be calculated for SDAI, CDAI, DAS28-ESR, DAS28-CRP, tender joint count, swollen joint count, VAS (physician- and patient-reported), HAQ, CRP, ESR, MMP-3, RF, anti-CCP antibody, and mTSS, and their changes from baseline to each assessment timepoint. For mTSS at Week 48, changes from Week 24 will also be analyzed for the summary statistics. In addition, ARM-2 and ARM-3 will be compared in terms of changes from Week24 to Week 48 using a stratified analysis with country as a factor.

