1.2. Secondary Endpoints

[Efficacy]

- · SDAI remission rate at Week 24
- \cdot SDAI remission rate at Week 48 in MTX monotherapy group
- Percentage of disease activity category by SDAI, CDAI, DAS28-ESR and DAS28-CRP at each assessment timepoint
- SDAI, CDAI, DAS28-ESR, and DAS28-CRP at each assessment timepoint, and change from baseline to each assessment timepoint
- · ACR20, ACR50, and ACR70 response rate at each assessment timepoint
- Tender joint count, swollen joint count, VAS (physician- and patient-reported), HAQ, CRP, ESR, MMP-3, RF, and anti-CCP antibody at each assessment timepoint, and change from baseline and Week 24 to each assessment timepoint
- Modified total sharp score (mTSS) at each assessment timepoint, and change from baseline to each assessment timepoint
- · Structural remission (mTSS ≤0.5) rate at each assessment timepoint
- \cdot HAQ remission rate at each assessment timepoint

[Safety]

- Vital signs and laboratory values at each assessment timepoint, and change from baseline to each assessment timepoint
- Status of AE (Up to Week 24, and up to Week 48 for each ARM)
- 1.3. Exploratory Endpoints
 - Erythrocyte MTX-PG concentration at Weeks 0, 4, 8, 12, 24, 36, and 48
 - Blood cytokine (IL-6, VEGF) at Weeks 0, 24, and 48
 - Plasma micro RNA at Week 24
 - · Serum anti-adalimumab antibody at Weeks 24 and 48

2. Considerations for Statistical Analysis

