2.3. Handling of Study Data

- · Fixed data after the completion of follow-up will be used for statistical analyses.
- For subjects who were enrolled more than once, statistical analyses will be conducted by removing the data that became unnecessary.
- Data handling meeting will be held prior to the database lock to discuss and determine how to handle individual data after removing the information on which treatment arm each subject was randomized to.
- For clinical laboratory values that exceed or fall below detection limits, detection limits will be substituted for actual values.
- As a rule, baseline is defined as Week 0. If the value at Week 0 is missing or not measured, the time of screening is regarded as baseline.
- · Change and percentage change are defined as follows:

Change = measured value after intervention – measured value at baseline Percentage change = (change/measured value at baseline) x 100 (%)

- 2.4. Handling of Missing Values
 - Subjects with missing data at an assessment time point of SDAI remission, ACR20, ACR50, and ACR70 response, HAQ remission, and structural remission due to study discontinuation or other relevant reasons will be considered as a "non-responder" at the time point of missing data.
 - Subjects with missing data at an assessment time point of CDAI, DAS28-ESR, DAS28-CRP remission due to study discontinuation or other relevant reasons will be considered as a "non-responder" at the time point of missing data.
 - Any missing data on SDAI, CDAI, DAS28-ESR, and DAS28-CRP will be considered as missing at the time point of missing data.

If there is a missing data on the assessment of SDAI, CDAI, DAS28-ESR, DAS28-CRP, and mTSS, the sensitivity analysis of GEE or MMRM method will be performed. If the result does not converge, a missing data will be imputed with the last observation carried forward (LOCF). In addition, for the sensitivity analysis of primary endpoint, a missing data on the final scheduled visit will be imputed with data on End of Study.

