The frequency of and the proportion of subjects classified into each disease activity category by SDAI, CDAI, DAS28-ESR and DAS28-CRP at each assessment timepoint will be calculated for each ARM (ARM-1, 2, or 3). Furthermore, Mantel-Haenszel test (risk difference) with country as a stratification factor will be performed to compare low disease activity and remission rate at each assessment timepoint between ARM-2 and ARM-3, and calculate the estimate of difference between the treatment arms and its two-tailed 95% confidence interval.

6.2.7. Tender joint count, swollen joint count, VAS (physician- and patient-reported), HAQ, CRP, ESR, MMP-3, RF, and anti-CCP antibody at each assessment timepoint, and change from baseline to each assessment timepoint

Descriptive statistics for tender joint count, swollen joint count, VAS (physician- and patient-reported), HAQ, CRP, ESR, MMP-3, RF, and anti-CCP antibody at each assessment timepoint and their changes from baseline to each assessment timepoint will be calculated for each ARM (ARM-1, 2, and 3). Furthermore, analysis of covariance (ANCOVA) adjusted by country will be performed to compare changes from baseline to Week 48 between ARM-2 and ARM-3, and calculate the estimate of difference between the treatment arms and its two-tailed 95% confidence interval.

6.2.8. Modified total sharp score (mTSS) at each assessment timepoint, and change from baseline to each assessment timepoint

Descriptive statistics for mTSS at each assessment timepoint and change from baseline to each assessment timepoint will be calculated for each ARM (ARM-1, 2, and 3). Furthermore, analysis of covariance (ANCOVA) adjusted by country will be performed to compare changes from baseline to Week 48 between ARM-2 and ARM-3, and calculate the estimate of difference between the treatment arms and its two-tailed 95% confidence interval. As with changes from baseline, descriptive statistics for changes from Week 24 to Week 48 will also be calculated for each ARM (ARM-1, 2, and 3). Furthermore, analysis of covariance (ANCOVA) adjusted by country will be performed to compare changes from Week 24 to Week 48 will also be calculated for each ARM (ARM-1, 2, and 3). Furthermore, analysis of covariance (ANCOVA) adjusted by country will be performed to compare changes from Week 24 to Week 48 between ARM-2 and ARM-3, and calculate the estimate of difference between the treatment arms and its two-tailed 95% confidence.

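### SAP 1.2 lists change from Week 24, but 6.2.7 never produces it; the ARM-2 versus ARM-3 ANCOVAs in 6.2.5 and 6.2.7 leave out the pre-randomization Week 24 value

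*SAP*

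**What the plan says.** **Endpoint lists.** For the joint counts, VAS, HAQ and laboratory markers, Protocol 4.1.2 names change from baseline only: "MMP-3, RF, and anti-CCP antibody at each assessment timepoint, and change from baseline to each assessment timepoint". SAP 1.2 goes further for the same variables: "change from baseline and Week 24 to each assessment timepoint". For SDAI, CDAI and the two DAS28 indices, both lists name change from baseline only.

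**Definitions.** SAP 2.3: "As a rule, baseline is defined as Week 0", with the screening value as fallback. Change is defined there only against baseline.

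**Analyses.** The descriptive part of SAP 6.2.7 reads "anti-CCP antibody at each assessment timepoint and their changes from baseline to each assessment timepoint will be calculated for each ARM". Its comparison of the arms, worded identically in 6.2.5 for the indices, is "analysis of covariance (ANCOVA) adjusted by country will be performed to compare changes from baseline to Week 48 between ARM-2 and ARM-3". The mixed-model sensitivity analysis in 6.2.5 is also expressed as change from baseline. Only mTSS, in 6.2.8, has a Week 24 to Week 48 analysis.

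**Protocol analysis text.** Protocol 9.2.1.2 says "For mTSS at Week 48, changes from Week 24 will also be analyzed for the summary statistics". The next sentence says "ARM-2 and ARM-3 will be compared in terms of changes from Week24 to Week 48 using a stratified analysis with country as a factor", without naming the variables it covers.

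**Timing.** Under Protocol 4.3.1 the site finishes the Week 24 assessments and enters the 28-joint counts, both VAS scores, CRP and the MTX dose in IWRS. Then: "If all necessary information is entered, a relevant treatment group in line with the status of randomization" is issued. SAP 9.1 records no revision from the protocol.

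**The concern.** There are two separate issues.

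First, an endpoint declared in SAP 1.2 has no analysis behind it. Because SAP 2.3 fixes baseline at Week 0, the wording of 6.2.7 cannot be stretched to cover change from Week 24. If the gap stays, someone will have to decide after the data are in whether and how to produce it. The trial is open-label and, under SAP 2.8, makes no multiplicity adjustment.

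Second, ARM-2 and ARM-3 share their first 24 weeks of MTX and diverge only after Week 24. The Week 24 value is the last measurement before allocation and would usually be expected to predict Week 48 better than Week 0 does. Comparing the arms on change from Week 0, with country as the only stated adjuster, gives up that information. It also leaves a chance imbalance at Week 24 uncorrected. The SAP does not say whether any starting value of the outcome is in the model. What is at stake is the width of the intervals for secondary continuous outcomes.

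**Working it through.** **Step 1: which variables have the mismatch.**
- Joint counts, VAS, HAQ, CRP, ESR, MMP-3, RF: SAP 1.2 lists change from Week 24; the heading, descriptive statistics and ANCOVA of 6.2.7 do not contain it.
- Anti-CCP: same mismatch. In the Protocol 7.5 schedule it is taken at screening and optionally at Week 48, so a change from Week 24 cannot be calculated.
- SDAI, CDAI, DAS28-ESR, DAS28-CRP: SAP 1.2, Protocol 4.1.2 and SAP 6.2.5 agree on change from baseline. No mismatch.
- mTSS: 6.2.8 analyses change from Week 24 although SAP 1.2 does not list it. Nothing is lost.

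**Step 2: where Week 24 does appear.** In 6.2.5 and 6.2.7 it is one of the summarized timepoints, and in the 6.2.5 mixed model it is one of the repeated outcomes. In neither ANCOVA is it named as the reference value or as a covariate.

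**Step 3: precision.** The plan states no figure to reproduce and gives no SDs or correlations, so the following are assumptions for the randomized subjects: r(0,48) = a = 0.1 to 0.3; r(24,48) = b = 0.4 to 0.6; r(0,24) = c = 0.2 to 0.5. The Week 48 SD is set to 1.

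Residual variance at Week 48:
- Week 0 value as covariate: 1 − a²
- Both values as covariates: 1 − (a² + b² − 2abc)/(1 − c²)

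Smallest gain on the grid (a = 0.3, b = 0.4, c = 0.5):
- Week 0 only: 1 − 0.09 = 0.91
- Both: 1 − (0.09 + 0.16 − 0.12)/0.75 = 0.827
- Ratio: 0.91/0.827 = 1.10; CI width ratio √1.10 = 1.05

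Largest gain (a = 0.1, b = 0.6, c = 0.5):
- Week 0 only: 1 − 0.01 = 0.99
- Both: 1 − (0.01 + 0.36 − 0.06)/0.75 = 0.587
- Ratio: 0.99/0.587 = 1.69; CI width ratio √1.69 = 1.30

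With the planned 110 per arm, all observed, the 95% half-width is 1.96 × √(2 × variance/110). It falls from 0.252 to 0.240 SD in the first case and from 0.263 to 0.202 SD in the second.

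**Step 4: unfavourable correlations.** Suppose Week 0 predicts Week 48 better than Week 24 does (a = 0.5, b = 0.4).
- Replacing Week 0 by Week 24 would lose precision: 0.75/0.84 = 0.89.
- Adding Week 24 beside Week 0 does not. At c = 0.5 the variance is 1 − (0.25 + 0.16 − 0.20)/0.75 = 0.72 and the ratio 0.75/0.72 = 1.04. At c = 0.2 it is 1 − (0.25 + 0.16 − 0.08)/0.96 = 0.656 and the ratio 0.75/0.656 = 1.14.

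This is the reason to add the Week 24 value and not to swap it in.

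**Step 5: one estimate, not two.** With both starting values in the linear model, subtracting either from the Week 48 outcome only shifts that value's own coefficient by 1. The arm coefficient is unchanged. In simulations with 220 subjects and three countries the two change scores gave arm estimates equal to within 1e-14. All estimators averaged 0.298 to 0.305 against a true difference of 0.3. With r(0,24) = 0.35, the variance ratios (Week 0 only to both) were 1.11 at a/b of 0.3/0.4, 1.59 at 0.1/0.6 and 1.07 at 0.5/0.4.

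**The case against.** The strongest reply is that only the mismatch between SAP 1.2 and 6.2.7 is a defect, and that the rest is an efficiency preference. For 6.2.5 that is right: the section does what SAP 1.2 and Protocol 4.1.2 say. The size of the gain rests on assumed correlations. Both arms start adalimumab at Week 24, which could weaken the Week 24 to Week 48 correlation. All randomized subjects have Week 24 SDAI above 3.3, which narrows its range and points to the low end for that index. The mismatch alone could be closed by deleting the words about Week 24 from SAP 1.2. And a separate set of Week 24 comparisons would add about 13 contrasts (four indices plus nine variables) and leave two competing estimates of one arm difference. All of this stands. It is why the repair is a single model and not a second comparison.

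Four stronger readings are tempting and are not supported.
- *The SAP departs from the protocol without recording it.* A reader might infer this from Protocol 9.2.1.2 and the empty SAP 9.1. But the sentence on Week 24 to Week 48 directly follows one about mTSS, and 6.2.8 carries it out for mTSS. The paragraph as a whole covers all the continuous variables, so the broad reading is possible, but it is not established.
- *The SAP ignores Week 24.* It does not; see Step 2. SAP 2.4 also plans GEE or MMRM for the indices when data are missing.
- *The planned contrast is biased.* Allocation follows Week 24, so with complete data it is not. Dropout could bias it, since Protocol 5.3 ties withdrawal after Week 24 partly to the arm's MTX dose. That would affect a Week 24 anchored analysis as well.
- *The variance is inflated almost fourfold.* One can reach 2.43/0.64 = 3.80, but only if the planned model holds no starting value at all and the Week 0 SD is 1.3 times the later SD (1.69 + 1 − 2 × 0.1 × 1.3 = 2.43). That figure mixes the choice of reference point with the absence of a covariate. The name ANCOVA suggests that some continuous covariate is intended, although the SAP names none.

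**Conclusion.** The point holds in two parts. Change from Week 24 is declared in SAP 1.2 and analysed nowhere in 6.2.7, and for anti-CCP it cannot be calculated; this needs no assumption. In 6.2.5 and 6.2.7 the comparisons of ARM-2 and ARM-3 leave out the Week 24 value as reference or covariate and do not state their covariates beyond country. Under the assumed correlations this costs a variance 1.10 to 1.69 times larger than with both values in the model (intervals 1.05 to 1.30 times as wide), and still 1.04 to 1.14 times in the unfavourable case. These ratios take the Week 0 value as already in the planned model and assume all 110 subjects per arm are observed.

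The point is minor. It touches secondary continuous outcomes only. The primary non-inferiority analysis, the binary comparisons and the planned mTSS comparison are unaffected. No margin applies to these variables, and the continuous outcomes in 6.2.5 and 6.2.7 are not among the key secondary endpoints in the protocol synopsis.

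**What to change.** 1. In SAP 6.2.5 and 6.2.7, for every variable except anti-CCP, specify one ANCOVA at Week 48 with arm, country, the Week 0 value (the SAP 2.3 baseline) and the Week 24 value. State that its arm difference applies to change from Week 0 and change from Week 24 alike. If SAP 2.5 leads to a transformation, put both starting values on the same scale as the outcome. For anti-CCP, state which covariates are used.
2. Add descriptive change from Week 24 to 6.2.7, and define it in SAP 2.3.
3. Remove anti-CCP from the Week 24 change in SAP 1.2.
4. Clarify whether the Week 24 to Week 48 sentence in Protocol 9.2.1.2 covers mTSS only or all the continuous variables. If all, record the difference in SAP 9.1.

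The cost is SAP wording and minor programming. No new data are needed: Week 24 is an essential visit for every listed variable except anti-CCP. The items entered in IWRS before an arm is issued already give SDAI, CDAI and DAS28-CRP at Week 24 for every randomized subject. No additional comparison arises, so there is no added multiplicity.

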## 2.1.2 Comorbidities related to the indication

RA causes pain, joint fracture, and joint degeneration due to destructive polyarthritis that chronically occurs all over the body. Inflammation, if persists, causes not only pain but also irreversible destructions in the joints, resulting in remarkable reduction of ADL. RA is known to be accompanied by not only joint symptoms but also a high frequency of extracapsular symptoms such as scleritis, airway lesion, interstitial pneumonia, pleurisy, vasculitis, secondary Sjogren's syndrome, and secondary amyloidosis. Pulmonary lesions particularly affect vital prognosis, and often causes acute exacerbation. Furthermore, RA patients are known to have poorer vital prognosis compared to general population due to persistent inflammation and immunological abnormality which are risk factors of arteriosclerosis and malignant disease (Wolfe F, et al. 1994: 481-94). Also, immunosuppression associated with typical treatment is a high risk factor of infection-related complications.

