## 2.1.3 Prognostic factors of the indication

Seropositive (rheumatoid factor and anti-CCP antibody), high disease activities, and bone erosion in early stage of disease are prognostic factors of future joint destruction, (Vastesaeger N, et al. 2009: 1114-21, Visser K, et al. 2010: 1333-7), and thus, are poor prognostic factors. Moreover, as mentioned above, the presence of interstitial pneumonia, vasculitis, and other extracapsular symptoms, and persistent inflammation are risk factors of arteriosclerosis and malignant disease. In addition, immunosuppression associated with typical treatment can cause serious infection, and thus can be a determining factor of prognosis.

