#### 7.2 Efficacy assessments

#### 7.2.1 X rays of hands and feet

In accordance with the assessment schedule presented in the following table, X rays of subjects' hands and feet will be performed at screening, and Weeks 24 and 48 (or at early termination). The X-rays of the hands and feet are unnecessary to be performed for early termination if early termination occurs within 28 days after the last X-rays. The X-ray image of the hands and feet should be sent to the study secretariat along with the subject ID. The X-ray image of the hands and feet will be independently reviewed by the X-ray Imaging Review Committee to evaluate bone erosions in the regions specified on the left side of the figure shown below, and also to evaluate joint space narrowing in the results will be sent to the data center.

Bone erosions will be evaluated for each region in accordance with the following score:

Score 1: Small bone erosion

Score 2: Large bone erosion (Not extend over the imaginary middle of the bone)

Score 3: Large bone erosion (Extends over the imaginary middle of the bone)

Score 5: Complete collapse of the joint

The score will be 0 to 5 for each hand region, and 0 to 10 for each foot region. The maximum total erosion score of both hands will be 160 points, and that of both feet will be 120 points.

Joint space narrowing will be evaluated for each region in accordance with the following score:

Score 1: Localized or merely suspected

Score 2: Generalized narrowing (≥50% joint space remaining)

Score 3: Generalized narrowing (≤50% joint space remaining) or subluxation

Score 4: Disappearance of joint space, or anchylosis or luxation

The maximum total joint space narrowing score of both hands will be 120 points, and that of both feet will be 48 points.

Source: Swinkels HL, et al. 2001: 176-90

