6.2.9. Structural remission (mTSS ≤0.5) rate at each assessment timepoint Structural remission rate and its two-tailed 95% confidence interval at each assessment timepoint will be calculated for each ARM (ARM-1, 2, and 3). Furthermore, Mantel-Haenszel test (risk difference) with country as a stratification factor will be performed to compare structural remission rates at Week 48 between ARM-2 and ARM-3, and calculate the estimate of difference between the treatment arms and its two-tailed 95% confidence interval.

7. Safety Analysis

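### Structural remission is defined as an absolute mTSS of 0.5 or less, so damage present before randomization caps the rate and dilutes the ARM-2 versus ARM-3 comparison

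*SAP*

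**What the plan says.** Protocol 4.1.2 lists "Structural remission (mTSS $\leq 0.5$ ) rate at each assessment timepoint" among the secondary endpoints. SAP 1.2 and SAP 6.2.9 repeat it as "Structural remission (mTSS ≤0.5) rate at each assessment timepoint". SAP 6.2.9 then plans a Mantel-Haenszel risk difference, stratified by country and with a 95% confidence interval, to "compare structural remission rates at Week 48 between ARM-2 and ARM-3". Neither document gives a reference visit for the 0.5 threshold. Where change is meant, the plan writes it: the neighbouring mTSS endpoint in Protocol 4.1.2 and SAP 1.2 names change from baseline, and SAP 6.2.8 names change from baseline and from Week 24.

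Other relevant text:

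- **Scoring (Protocol 7.2.1).** The lowest listed erosion grade is "Score 1: Small bone erosion"; the lowest listed joint-space grade is "Score 1: Localized or merely suspected".
- **Disease course (Protocol 2.1.2).** Persistent inflammation "causes not only pain but also irreversible destructions in the joints".
- **Randomization (Protocol 4.3.1).** Allocation to ARM-2 or ARM-3 comes "Upon completion of Week 24 assessments", after 24 weeks of MTX alone.
- **Population (Protocol 5.1 and 5.2).** Patients may be up to 2 years from diagnosis, and existing erosions are not an exclusion.

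**The concern.** mTSS is cumulative. A level at Week 48 combines damage from before the study, damage during the 24 weeks of MTX alone, and damage after randomization. Only the last can differ between ARM-2 and ARM-3 because of the assigned treatment. A subject who enters the randomized period with one small erosion is a non-responder at Week 48 whatever happens afterwards, and so adds to the denominator without being able to show a treatment effect.

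The trial seeks to show that a reduced MTX dose is not worse. A structural endpoint that shrinks any real difference makes the arms look alike for reasons unrelated to treatment. The resulting rate would also be hard to read beside the change analysis in SAP 6.2.8.

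**Working it through.** **Plan's own figure.** The documents state no rate, effect size or power for structural remission, so there is none to reproduce. The only design input used is 110 subjects per arm (Protocol 9.4.1), with the two-sided 5% level of SAP 2.6.

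**What the threshold means.** The maxima in Protocol 7.2.1 are 160 (hand erosion), 120 (foot erosion), 120 (hand narrowing) and 48 (foot narrowing): 160 + 120 + 120 + 48 = 448. All listed regional scores are whole numbers and the smallest above zero is 1. A single-reading total of 0.5 or less is therefore a total of 0.

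**Cap.** Let *d* be the share of randomized subjects with any damage at Week 24. If damage does not reverse, the Week 48 rate in either arm cannot exceed 1 − *d*.

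**Attenuation, equal progression.** Let *r* be the proportion without progression from Week 24 to Week 48, the same in damaged and undamaged subjects. The rate as written is (1 − *d*)·*r*, so the difference is (1 − *d*)(*r*₂ − *r*₃). Power is Φ(|*p*₂ − *p*₃|/SE − 1.96), with SE = √[*p*₂(1 − *p*₂)/110 + *p*₃(1 − *p*₃)/110], ignoring the country strata.

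The values of *r* and *d* below are assumptions. Protocol 2.1.1 cites erosion in about 70% of patients within 2 years without appropriate treatment. That is not an estimate for this population and serves only as the upper end of the range.

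Assumed *r* = 85% versus 70%:

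| *d* | Rates (%) | Difference (points) | Power |
|---|---|---|---|
| change-based | 85.0 v 70.0 | 15.0 | 77% |
| 10% | 76.5 v 63.0 | 13.5 | 60% |
| 30% | 59.5 v 49.0 | 10.5 | 35% |
| 50% | 42.5 v 35.0 | 7.5 | 21% |
| 70% | 25.5 v 21.0 | 4.5 | 12% |

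Example, *d* = 30%: SE = √[(0.595 × 0.405 + 0.49 × 0.51)/110] = 0.0668; 0.105/0.0668 − 1.96 = −0.39; Φ = 0.35.

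With assumed *r* = 90% versus 80%, change-based power is 55.5%. As written it is 35%, 18%, 11% and 7% at the same four values of *d*.

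**Attenuation, unequal progression.** Protocol 2.1.3 says that "bone erosion in early stage of disease are prognostic factors of future joint destruction". Suppose damaged subjects progress twice as often as undamaged ones, with overall progression of 15% versus 30%. Progression among the undamaged is then overall/(1 + *d*), and the difference is 0.15 × (1 − *d*)/(1 + *d*):

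- *d* = 10%: 0.15 × 0.9/1.1 = 12.3 points, power 53%
- *d* = 30%: 0.15 × 0.7/1.3 = 8.1 points, power 23%
- *d* = 50%: 0.15 × 0.5/1.5 = 5.0 points, power 11%
- *d* = 70%: 0.15 × 0.3/1.7 = 2.6 points, power 6.5%

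The loss is larger here than under equal progression.

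**The case against.** **The structural question is answered elsewhere.** SAP 6.2.8 and Protocol 9.2.1.2 already compare mTSS change from Week 24 to Week 48. The responder rate is not a key secondary endpoint in the synopsis and carries no multiplicity control or stated power. This stands and limits the impact, but SAP 6.2.9 would still produce a formal comparison that is hard to interpret.

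**The size is invented.** No structural difference is hypothesised, and with equal non-progression there is nothing to attenuate. It is true that the figures are illustrative. The cap and the direction of the attenuation do not depend on them.

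**The 77% starting point is generous.** SAP 2.4 counts missing structural data as non-response. With 10% or 20% of films missing in each arm (also an assumption), change-based power at 85% versus 70% is 60% or 46%. At *d* = 30% the level definition then gives 29% or 24%. The contrast narrows but remains clear.

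**The premises are softer than they look.** How several readings are combined is not stated, irreversibility is background text rather than a scoring rule, and suspected narrowing can be rescored. The cap is therefore approximate.

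**Change from Week 24 cannot serve every timepoint.** At Week 24 it is zero for everyone. This is correct, and the remedy has to name two windows.

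**Conclusion.** The concern holds. As written, structural remission is a level that subjects damaged before randomization essentially cannot meet, so the Week 48 rate is capped near 1 − *d*. Under equal progression the difference between arms shrinks by the factor 1 − *d*; if damaged subjects progress faster, it shrinks further. Randomization after Week 24 balances earlier damage in expectation, so the comparison is not biased by imbalance. What is lost is precision relative to the effect.

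The size cannot be derived from the documents. Over assumed shares of 10% to 70% damaged, a 15-point difference becomes 13.5 to 4.5 points under equal progression. The conclusion rests on the whole-number scores, on damage not reversing, and on some subjects having damage at Week 24. If the line was meant as shorthand for a change, the correction is editorial, but it is still needed: screening and Week 24 as reference visits give different responders.

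**What to change.** In Protocol 4.1.2, SAP 1.2 and SAP 6.2.9, define structural remission as a change in mTSS of 0.5 or less, and name each version by its window:

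- **Week 24 to Week 48** for the Mantel-Haenszel comparison of ARM-2 with ARM-3, matching the window in SAP 6.2.8.
- **Screening to Week 24 and screening to Week 48** for description by arm, including ARM-1.

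State that a subject lacking either film needed for the change is a non-responder, in line with SAP 2.4. If the absolute level is wanted, report it descriptively only, labelled as no radiographic damage.

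No new data are needed: hand and foot X-rays at screening, Week 24 and Week 48 are already scheduled and scored. The cost is wording in three places before the final analysis. The Protocol 4.1.2 edit is a protocol amendment and, under Protocol 1.1.3, takes effect only after Certified Review Board approval and entry in jRCT.
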